Statistical Analysis Plan

Use of abdominal binder in colonoscopies performed by trainees in
Gastrointestinal Endoscopy: A randomized, double-blind, sham-
controlled trial

NCT05617521

09/24/2023

Sample size was estimated over the primary outcome of the study based on pre-experimental data estimation and previously reported CIT and SD of similar studies with fellows' participation. It was calculated that 142 participants were needed to detect a 60-second difference in CIT (SD 110 sec), with 90% power and two-side alpha 0.05. Moreover, it was also calculated based on the frequency of ancillary maneuvers, using pre-experimental data estimation and literature data. It was found that 186 participants (93 per group) were needed to detect a 20% reduction in the use of ancillary maneuvers, with 90% power and two-side alpha 0.05. As a preventive measure in case of withdrawal or exclusion, the sample was expanded by 10%, a total of 206 patients, 103 in each group were included in the study.

Descriptive statistical analysis, including mean, mode, and frequencies will be performed for the description of the study data. The comparative analysis of the quantitative data will be previously subjected to normality evaluation by the Shapiro–Wilk test and graphical analyses. According to the normality, data comparative analysis will be performed either with a two-way Student's test or U Mann–Whitney test. For the comparative analyses of the categorical data (e.g., manual abdominal compression, postural change, need of intervention by the attending endoscopist) will be used chi-square or Fisher' exact test. A p value of <0.05 will be accepted as statistical significance. Statistical inferential analysis will be performed using RStudio® (R Core Team v.1.2.5033; R Foundation for Statistical Computing, Vienna, Austria) and SPSS® Statistics for Windows Version 23.0 (IBM Corp., Armonk, NY, USA). RStudio® (R Core Team v.1.2.5033) will be also used for drawing graphics. The study biostatistician (SA) will be blinded to the randomization phase and recollection data process.

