Primary outcome of this study was CIT (the time from the scope insertion to intubation of the cecum and visualization of the appendiceal orifice and ileocecal valvule). Main secondary outcomes were the cecal intubation length (CIL), ileocecal valve intubation time (IVIT), manual abdominal compression or postural change requirement, and the need for intervention by the attending endoscopist during the procedure. Other secondary outcomes included colonoscopy completion rate, trainee-reported insertion difficulty, adenoma detection, need for extra analgesic drugs, patient-reported pain, and satisfaction level at discharge of the endoscopy area. Before to leave the recovery room, the patients were asked for pain using a 10-point visual analog scale (VAS), and for satisfaction using a 5-point scale (5= very satisfactory, 4= satisfactory, 3= unsatisfactory, 2= very unsatisfactory, 1= extremely unsatisfactory) by an assistant blinded to the study.

Planned *a priori* subgroup analyses included stratification according to age, gender, and BMI. Participants with incomplete colonoscopy were excluded from the primary outcome analysis (CIT) and two of the main secondary outcomes (CIL and IVIT) yet included for the rest of the secondary outcomes. Primary analysis method was intention-to-treat (ITT), including all randomized participants. A per-protocol (PP) analysis method was also performed, excluding participants in the AB group whose binder was removed or loosened at any time of the procedure.

Bibliography

3. Shahidi N, Ou G, Telford J, Enns R. Establishing the learning curve for achieving competency in

performing colonoscopy: A systematic review. *Gastrointest Endosc* [Internet]. 2014;80(3):410–6. Available from: <http://dx.doi.org/10.1016/j.gie.2014.04.056>

4. Cheng W Bin, Moser MAJ, Kanagaratnam S, Zhang WJ. Analysis of and mathematical model insight into loop formation in colonoscopy. *Proc Inst Mech Eng Part H J Eng Med*. 2012;226(11):858–67.

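### The primary CIT test is held at 5%, but the same p<0.05 rule covers ancillary maneuvers and all other analyses with no testing order, adjustment or exploratory label

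*SAP*

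**What the plan says.** **Outcomes (Protocol, Outcomes).** CIT is the single primary outcome. The next tier begins "Main secondary outcomes were the cecal intubation length (CIL), ileocecal valve intubation time (IVIT), manual abdominal compression or postural change requirement" and ends with intervention by the attending endoscopist, which makes four main secondary outcomes. Six other secondary outcomes follow: completion, trainee-rated difficulty, adenoma detection, extra analgesia, pain and satisfaction. The same section plans subgroups by age, gender and BMI, and a per-protocol analysis beside the primary intention-to-treat analysis.

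**Sample size (SAP, first paragraph).** The paragraph opens "Sample size was estimated over the primary outcome of the study" and states that "142 participants were needed to detect a 60-second difference in CIT (SD 110 sec), with 90% power and two-side alpha 0.05". It then sizes the trial again: "186 participants (93 per group) were needed to detect a 20% reduction in the use of ancillary maneuvers", also at 90% power and two-sided 0.05. The larger figure is carried forward and raised to 206.

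**Decision rule (SAP, second paragraph).** "A p value of <0.05 will be accepted as statistical significance". It is tied to no outcome. Neither document gives an order of testing, a multiplicity adjustment, or a statement that secondary results are exploratory.

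**The concern.** Ancillary maneuvers are formally a main secondary outcome, but they have their own 90% power calculation and they determine N. A reader would expect a formal claim about them, yet nothing says whether that claim depends on CIT. The other nine secondary outcomes fall under the same threshold, as do the subgroups and the per-protocol repeats.

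The hypothesis in the protocol introduction is broad: that the binder makes colonoscopy easier and more effective for inexperienced operators. If CIT were null and maneuver use, insertion length or attending intervention crossed 0.05, the plan as written would allow that result to be declared significant and read as support for the hypothesis. What is at stake is how such a secondary result may be described, not the validity of the CIT test.

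**Working it through.** **1. Reproduce the plan's own figure.** Inputs from the SAP: difference 60 s, SD 110 s, 90% power, two-sided 0.05.

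n per arm = 2(1.960 + 1.282)² × (110/60)² ≈ 2 × 10.51 × 3.361 ≈ 70.6, so 71 per arm and 142 in total. This matches the SAP. The CIT test therefore has the full two-sided 0.05.

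**2. The second sizing.** No control rate for ancillary maneuvers is given, so 93 per arm can only be back-solved. With an absolute 20-point reduction and no continuity correction, control rates of 0.33 and 0.34 give 91 and 94 per arm, and 0.87 and 0.86 give the same pair. With a relative 20% reduction, a control rate of 0.91 gives 92. The figure is attainable at the full two-sided 0.05, so no alpha was shared between the two endpoints.

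**3. Count the tests.** 1 primary + 4 main secondary + 6 other secondary = 11. The SAP lists manual compression and postural change as separate categorical comparisons; counted that way there are 12.

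**4. Chance of at least one p<0.05 when no outcome differs.**

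- Independent tests: 1 − 0.95^k.
- Common correlation ρ between normal test statistics: 1 − ∫ φ(x) [Φ(a) − Φ(b)]^k dx, with a = (1.96 − √ρ·x)/√(1−ρ) and b = (−1.96 − √ρ·x)/√(1−ρ).

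The documents give no correlations, so ρ is an assumption and a range is shown.

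| Tests | ρ = 0 | ρ = 0.3 | ρ = 0.5 | ρ = 0.8 | ρ = 0.9 |
|---|---|---|---|---|---|
| CIT alone (k = 1) | 5.0% | 5.0% | 5.0% | 5.0% | 5.0% |
| Two sized endpoints (k = 2) | 9.8% | 9.5% | 9.1% | 7.8% | 7.0% |
| CIT + 4 main secondary (k = 5) | 22.6% | 20.9% | 18.3% | 12.7% | 10.2% |
| All outcomes (k = 11) | 43.1% | 37.5% | 30.4% | 18.0% | 13.1% |
| Compression and position separate (k = 12) | 46.0% | 39.7% | 31.9% | 18.6% | 13.5% |

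The per-protocol repeats and subgroups are not counted and would add to these figures.

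**5. Direction.** The table counts rejections either way. For a false finding in favour of the binder only, under independence: 1 − 0.975² = 4.9% for the two sized endpoints and 1 − 0.975¹¹ = 24.3% for 11 outcomes.

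**6. What a fixed sequence would cost in power.** Ancillary maneuvers lose power only when CIT fails. Under the SAP's own CIT assumptions, CIT power is 96.1% at 93 per arm and 97.5% at 103 per arm. The loss is then at most 100 − 96.1 = 3.9 points, or 100 − 97.5 = 2.5 points. Splitting alpha equally would cost more: at 0.025 each, and assuming 0.34 against 0.14 for maneuvers, 222 participants would be needed before any dropout allowance, against 94 × 2 = 188 at 0.05.

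**The case against.** The strongest reply is that the plan already has one primary outcome, tested once at 5%, and that secondary outcomes cannot change that rate. This is correct. Several stronger readings are tempting, and the documents do not support them.

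- *Sizing on two endpoints inflates type I error.* It does not. It sets N to the larger requirement, 186 rather than 142, and gives CIT more power.
- *CIT and ancillary maneuvers are co-primary, so the trial runs at 9.8%.* Neither document says so, or says that a win on a secondary outcome would count as success. The 9.8% applies only if a win on either would be claimed.
- *The trial has a 43% chance of a false claim.* That figure assumes independence and counts results favouring the sham. CIT, valve intubation time, insertion length, maneuvers, attending intervention and difficulty all describe the same insertion, so positive correlation is likely.

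It can also be said that the outcomes are already ranked as primary, main secondary and other secondary, and that the SAP sentence is a generic threshold. Both are fair. But a ranking without a consequence is not a testing rule, and nothing in the SAP limits the threshold to CIT. Fisher's exact test, which the SAP allows, is conservative for sparse outcomes, so it would lower the figures somewhat.

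What remains of the concern is the missing rule for everything other than CIT.

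**Conclusion.** The point holds as an inexpensive clarification, not as a defect in the primary analysis. CIT is controlled at two-sided 5%. Error is not controlled for ancillary maneuvers, the other secondary outcomes, the per-protocol analysis or the subgroups, and the stated rule allows any of them to be called significant when CIT is not.

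If the binder has no effect, the chance of at least one nominal p<0.05 among the 11 outcomes exceeds 5% across the whole range examined, from 13.1% at ρ = 0.9 to 43.1% under independence. These figures assume that all nulls are true, that test statistics are approximately normal with one common correlation, and that the threshold applies to every listed outcome. The last is an inference from a sentence that names none.

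**What to change.** Replace the single threshold sentence in the SAP with the following:

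1. Test CIT at two-sided 0.05.
2. Only if CIT is significant, test ancillary maneuvers at two-sided 0.05. Define this as one composite yes/no variable: manual compression or postural change, as the Protocol's Outcomes section joins them. The SAP lists the two separately, so the gate cannot be applied until this is settled.
3. Report all other secondary outcomes, the per-protocol analysis and the subgroups as estimates with nominal p-values, labelled exploratory.

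This holds the chance of any false formal claim at 5%, leaves CIT's alpha and power unchanged and needs no added participants. The price is that ancillary maneuvers cannot be formally claimed if CIT is not significant. Declaring CIT alone confirmatory would also close the gap, but would leave the endpoint that sets N with no formal test.

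The SAP is dated 09/24/2023 and the protocol gives recruitment as ending in January 2023. The SAP and the report should therefore state when the sequence was added and whether outcome data had been seen by then. If they had, the same limits should still govern the wording of claims, but the sequence should not be presented as prespecified.
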